## 4.0 Randomization

There is no randomization as part of this study. This is a prospective observational multicenter study consisting of approximately 30 centers (Appendix 1). Each center enrolling patients will utilize a common diagnostic algorithm (Appendix 2), and then apply their explicitly defined standard of care. The patients will be prospectively tracked for outcomes with respect to disease recurrence, need for

additional surgery, tracheostomy, as well as subjective patient reported outcomes in breathing, voice, and swallowing.

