## 5.0 Study Procedures

**Recruitment and Enrollment:** We anticipate a sample size of 800-1100 patients recruited across the participating centers. The target goal for Vanderbilt recruitment is 750-800 patients. There are currently 40 confirmed participating sites that will contribute patients (additional centers may be added in protocol amendments provided they meet defined study site selection criteria). Participating centers include those across all regions of the U.S. and international sites in the UK. Many are academic centers that are tertiary referral centers for adult laryngotracheal stenosis (LTS) and thus have significant experience treating this rare condition. Nearly all LTS patients are ultimately referred for care and cluster at such high-volume centers, and thus we anticipate enrolling a representative patient cohort. Each research site has appropriate technological infrastructure for data collection and pathologic specimen tracking.

Study participants will be recruited via several mechanisms. Direct recruitment by participating clinician providers that diagnose and treat these patients will occur at each of the participating centers. It is expected that the majority of patients will be recruited through this approach. Patients will be identified by PI, Sub-I or Key study personnel and approached by a member of the research team at each institution regarding the study, or contacted by phone or email about the study. Participants may also be seen due to referrals in to participating sites/providers.

Additionally interested stakeholders can identify this study directly through its registration with ClinicalTrials.gov, the National Organization for Rare Disorders (NORD) website and rare disease database. Once recruited patients will undergo detailed discussion regarding risks and benefits of the trial, and informed consent will be obtained.

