Propensity scoring can only adjust for observed confounding variables such as those listed above not unobserved ones. Therefore, we will employ quantitative and limited variable (QLIM) to conduct instrumental variable analysis to adjust for unobserved confounding. The instrumental variable has to meet five specific assumptions: 1) potential outcomes for each patient are unrelated to treatment status of other patients, 2) instrument affects receipt of the treatment of interest, 3) this effect is always in the same direction, 4) instrument assigns treatment randomly, and 5) instrument has an effect on the outcome only through the treatment assignment. The instrument that we plan to use in this analysis is distance from the patient's residence to the treating facility. The assumption is that the association between distance to the hospital and time to recurrence is due only to the effect of relative distance on treatment assignment after controlling for observed variables and not directly correlated with time to recurrence. This process will involve a two-stage process that first uses the instrument variable and other covariates to predict the treatment. A second stage estimates the outcome by the predicted treatment (from the first model) and other covariates. Using a two-stage approach has the advantage of incorporating the predicted treatment into the outcome model as it represents the portion of treatment selection related to distance from the treating facility. We will also adjust, when possible, for any instrument-outcome confounding, as confounding can still occur even with the instrumental variable procedure. Other instruments will be considered if distance to treating facility is not found to meet the aforementioned assumptions or is found to significantly confound the outcome.

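### Distance to the treating facility is set jointly with treatment, so the planned instrumental-variable estimate can be more biased or far less precise than no adjustment

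*Combined protocol and SAP*

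**What the plan says.** Section 12.0 (strategy to address confounding by selection bias) assigns observed confounding to propensity scores and unobserved confounding to an instrumental variable. The instrument is named as follows: "The instrument that we plan to use in this analysis is distance from the patient's residence to the treating facility".

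The plan lists five conditions for a valid instrument. The second is relevance: the instrument must influence which treatment is received. The fourth is "instrument assigns treatment randomly". The fifth is "instrument has an effect on the outcome only through the treatment assignment". The plan then describes the assumed link between distance and the outcome in these words: "due only to the effect of relative distance on treatment assignment after controlling for observed variables and not directly correlated with time to recurrence". That is the only mention of relative distance, and no reference facility is given.

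There are two safeguards: adjustment for instrument-outcome confounding where this can be done, and a fallback, "Other instruments will be considered if distance to treating facility is not found to meet the aforementioned assumptions". No test or threshold is attached to either.

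Three other places bear on the point:
- Section 4.0 has the centres use a common diagnostic algorithm "and then apply their explicitly defined standard of care".
- Section 5.0 describes how patients reach centres: "Nearly all LTS patients are ultimately referred for care and cluster at such high-volume centers".
- The synopsis defines the primary endpoint through a repeat procedure.

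For Aim 2, Section 12.0 defines treatment at two levels: dilation against excision or open surgery.

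**The concern.** An instrument should be fixed before treatment and unrelated to the reasons for it. Distance to the treating facility is known only once a centre has treated the patient, and the centre largely determines the treatment. Three problems follow, and each touches a condition on the plan's own list.

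- **Relevance.** If patients attend the nearest centre, someone 5 miles from a dilation centre and someone 5 miles from an open-surgery centre have the same instrument value. Distance then says little about treatment.
- **Independence.** If patients are referred or travel to reach a particular treatment, the distance reflects severity, resources or preference. These are the unmeasured factors that the analysis is meant to remove.
- **Exclusion.** The event requires a further procedure. A long journey may delay it whatever the initial treatment was.

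This analysis is the plan's only stated protection against unobserved confounding. A distorted estimate from it would be read as the corrected one.

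**Working it through.** The documents give no first-stage strength, expected bias or power for this analysis, so there is no figure to reproduce. The check is algebra followed by simulation.

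**Algebra.** Let T be treatment (1 = non-dilation), Z the distance to the treating centre and U an unmeasured factor. Take the outcome as Y = βT + aU + γZ + error. In large samples:

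- unadjusted bias = [a·Cov(T,U) + γ·Cov(T,Z)] / Var(T)
- instrumental-variable bias = [a·Cov(Z,U) + γ·Var(Z)] / Cov(Z,T)

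Selection on U makes Cov(Z,U) non-zero, and a direct travel effect makes γ non-zero. Both are divided by Cov(Z,T), which is small when distance barely predicts treatment.

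**Simulation inputs.**
- From the documents: n = 1000, the sum of the group sizes listed in Section 12.0 (800 + 100 + 100); 40 centres (Section 5.0). The planned non-dilation share is 200/1000 = 20%.
- Assumed: β = 1, a = 0.5, noise SD 1, a linear uncensored outcome and no covariates. Centres and residences are uniform on a 10 × 10 square. Centre choice depends on distance, on a pull towards or away from non-dilation centres, on selection strength s times U, and on random noise. There are 3 or 6 non-dilation centres, and 300 or 400 replicates respectively.
- Differential distance is distance to the nearest non-dilation centre minus distance to the nearest other centre.

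Selected results, as medians (the 3-centre rows are those with the share closest to 20%):

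| Centres | s | γ | Share | Unadjusted bias | Planned IV bias (F) | Differential IV bias (F) | Planned IV error larger than unadjusted |
|---|---|---|---|---|---|---|---|
| 3 | 0 | 0 | 0.16 | 0.01 | -0.04 (2.4) | -0.01 (164.3) | 95% |
| 3 | 0.5 | 0 | 0.16 | 0.20 | 0.38 (3.0) | -0.01 (162.6) | 89% |
| 3 | 1 | 0 | 0.18 | 0.36 | 0.71 (7.5) | -0.01 (156.6) | 79% |
| 3 | 2 | 0 | 0.22 | 0.57 | 0.90 (30.9) | -0.01 (123.6) | 76% |
| 3 | 1 | 0.1 | 0.18 | 0.39 | 4.44 (7.5) | 0.00 (156.6) | 100% |
| 6 | 0.5 | 0 | 0.06 | 0.23 | 0.04 (1.0) | -0.04 (40.9) | 94% |
| 6 | 1 | 0 | 0.08 | 0.42 | 0.57 (0.7) | -0.03 (44.9) | 93% |
| 6 | 1 | 0.1 | 0.08 | 0.42 | -7.69 (0.7) | 0.17 (44.9) | 100% |

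Across all settings run:

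1. **Selection on U, γ = 0, 3 centres:** planned instrument 0.37 to 0.90, unadjusted 0.18 to 0.57.
2. **The same with γ = 0.05 to 0.2:** 1.40 to 9.60 against 0.20 to 0.67. The algebra explains the growth. At s = 1 the bias rises from 0.71 to 4.44 at γ = 0.1, and (4.44 - 0.71)/0.1 ≈ 37, so Var(Z)/Cov(Z,T) multiplies any direct effect about 37-fold.
3. **No selection and γ = 0:** median bias is -0.09 to 0.05, but the planned instrument's error exceeds the unadjusted error in 91% to 96% of replicates, through variance (F 0.8 to 16.4).
4. **Differential distance:** -0.14 to 0.03 with 3 centres. With 6 centres it is -0.04 to -0.03 at γ = 0, but 0.17 to 0.51 at γ = 0.1 to 0.2.

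Two further runs used other travel models. On the plan's contrast of dilation against resection or open surgery, under unmeasured selection, the planned instrument gave F of about 1 to 7 and median bias 0.54 to 0.86 (unadjusted 0.37 to 0.57). Differential distance gave bias of about 0 and F above 90. With every patient attending the nearest of 32 dilation, 4 resection and 4 open-surgery centres, median F for open surgery against the rest was 3.9 for the planned instrument and 339 for differential distance.

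**The case against.** The strongest reply is that relative distance may mean differential distance, which is the remedy proposed here. That reading is possible. However, the sentence naming the instrument, and the later references to it, speak of the treating facility, and no reference centre is defined. An analyst following the text would compute realised distance.

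The plan also lets another instrument replace distance. This stands in part: relevance is testable, so a weak first stage could be caught, although no threshold is set. Independence and exclusion cannot be verified from the data with one instrument. Adjustment reaches only measured factors, although the covariate list is long and includes geographic location.

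The sizes are assumed, and this stands in full. With another travel model and no direct effect, a U effect of 0.1 gave a bias of 0.09 SD against 0.07 unadjusted, while a U effect of 0.5 gave 0.48 against 0.24. The direction held, and the size followed the input.

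A reader might infer that one instrument is being asked to identify two contrasts among three treatments. The documents do not support that for this analysis: Section 12.0 gives Aim 2 a two-level treatment variable, and one instrument can serve one binary contrast. The three-group comparison there concerns the propensity-matched groups.

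**Conclusion.** The concern holds in conditional form. As named, the instrument is set jointly with treatment, and the resulting estimate can be more biased or far less precise than no adjustment. The magnitudes above are illustrations. They rest on an assumed U effect, travel model, direct distance effect and mix of centres, with no covariates and no censoring.

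Three stronger readings go too far:

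- **That the planned estimate must be worse in bias.** In one setting with selection (6 centres, s = 0.5, γ = 0) its median bias was 0.04 against 0.23 unadjusted, and the weakness was precision (F about 1).
- **That relevance, independence and exclusion all fail.** The relevance and independence failures come from different patterns of attendance. The documents describe referral and clustering but do not say which pattern dominates, or that patients themselves choose the centre.
- **That the main comparison is undermined.** Kaplan-Meier, logrank and Cox analyses and the propensity methods do not depend on this instrument.

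**What to change.** Define the instrument in Section 12.0 from residence and site locations alone. For the stated Aim 2 contrast, use distance from residence to the nearest participating centre whose standard is resection or open surgery, minus distance to the nearest participating dilation centre. If resection and open surgery are to be analysed separately, use one differential distance per contrast. Then:

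- remove the treating-facility wording, or define relative distance to match;
- report the first-stage F, with a threshold fixed in advance for calling the instrument weak;
- specify a second stage that handles censored times, such as two-stage residual inclusion in a survival model;
- label the result a sensitivity analysis and state that independence and exclusion are assumed.

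The cost is SAP wording, a distance calculation and a classification of sites by standard treatment. The classification will be inexact where a centre's practice is mixed, and intervals may be wide. A direct effect of travel on return for a procedure is not fully removed; recording repeat procedures done at any hospital would help limit it.

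### The instrument is distance to the facility that actually treated the patient, which is largely set together with the treatment; it should be defined without reference to the treating site

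*Combined protocol and SAP*

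**What the plan says.** All of the IV text is in section 12.0, under the strategy for confounding by selection bias.

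- **Instrument:** "distance from the patient's residence to the treating facility". The same paragraph refers twice more to distance to or from the treating facility.
- **Conditions:** five are listed. The fourth is "instrument assigns treatment randomly". The exclusion assumption is that any association of distance with time to recurrence is "due only to the effect of relative distance on treatment assignment after controlling for observed variables". Relative distance is not defined.
- **Estimator:** a two-stage model that "first uses the instrument variable and other covariates to predict the treatment", then relates the outcome to the predicted treatment and covariates.
- **Fallback:** "Other instruments will be considered if distance to treating facility is not found to meet the aforementioned assumptions". No check, threshold or alternative is named.
- **Contrast:** the same strategy frames treatment as dilation against resection or open surgery combined.

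Three other places bear on how a patient comes to a facility and a treatment. Section 4.0 says centres will "apply their explicitly defined standard of care". The second hypothesis in section 12.0 compares time to recurrence between centres whose surgical approaches differ. Section 5.0 says "Nearly all LTS patients are ultimately referred for care and cluster at such high-volume centers".

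**The concern.** An instrument has to influence treatment without sharing its unmeasured causes. Distance to the treating facility is known only once the patient has a treating facility. Where centre and approach go together, choosing or being referred to a centre largely settles both the treatment and the distance. The distance can then reflect whatever prompted the travel, such as severity or resources.

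The propensity analysis handles measured confounders only; the IV analysis is the plan's one answer to unmeasured ones. If the instrument carries the same selection, IV and propensity estimates can agree because both are biased, and a reader could take that agreement as evidence against hidden bias.

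**Working it through.** **1. The plan's own figures.** The plan gives no effect size, standard deviation, first-stage strength or power for the IV analysis, so there is no figure to reproduce. What follows is algebra plus simulation under stated assumptions.

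**2. Why the bias can survive.** Let T be treatment (1 = resection or open, 0 = dilation), Z the distance to the treating site, and e the part of log time to recurrence not due to treatment. In large samples

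IV estimate = true effect + Cov(Z, e) / Cov(Z, T).

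Suppose Z is related to e only through T, with mean distance m1 when T = 1 and m0 when T = 0. Then Cov(Z, e) = (m1 − m0) Cov(T, e) and Cov(Z, T) = (m1 − m0) Var(T). The factor (m1 − m0) cancels, leaving

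IV bias = Cov(T, e) / Var(T),

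which is the bias of the unadjusted comparison. A large m1 − m0 raises the first-stage F and leaves the bias unchanged.

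**3. Simulation inputs.**
- From the documents: 40 sites (section 5.0); groups of about 800, 100 and 100 (Sample Size Considerations), so N = 1000 and (100 + 100)/1000 = 20% not on dilation; two-sided 5% test.
- Assumed: random map; 8 of the 40 sites non-dilation; unmeasured severity U with effect −0.5 on log time; total SD about 1; linear two-stage least squares; no censoring; no measured covariates; 2000 runs per cell. U is best read as what remains after measured adjustment.

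**4. Patients choose a treatment and travel to the nearest site offering it; true effect zero.**

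| Selection on U (logits per SD) | Unadjusted estimate | IV, treating-facility distance | False rejection | F | IV, differential distance | False rejection | F |
|---|---|---|---|---|---|---|---|
| 0 | 0.00 | −0.02 | 4.9% | 113 | −0.01 | 4.0% | 98 |
| 0.5 | −0.22 | −0.23 | 16% | 119 | −0.01 | 4.0% | 92 |
| 1 | −0.40 | −0.42 | 44% | 133 | −0.01 | 4.0% | 78 |
| 2 | −0.62 | −0.67 | 86% | 169 | −0.01 | 4.0% | 49 |

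Estimates are medians on the log-time scale. At selection 1, exp(−0.42) = 0.66: a treatment with no effect appears to shorten time to recurrence by about a third. With a true time ratio of 1.5 at the same selection, the written instrument gives a median of −0.01, so the benefit disappears; differential distance gives 0.40, against log 1.5 = 0.405.

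Other maps and milder confounding (U correlated 0.2–0.3 with log time, 1 logit per SD, 400–500 runs) gave IV estimates of −0.18 to −0.25 against −0.16 to −0.26 unadjusted, with 9–22% rejection. Rejection was 3–4% where distance dominated choice. At correlation 0.1, rejection stayed near 5% but the bias still equalled the unadjusted bias.

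**5. Everyone attends the nearest site and the site sets treatment.** The written instrument has median F 4.3, with power 3.6% for a time ratio of 1.5 and 9.1% for 2.0. Differential distance rejects in 4.4% under no effect, with power 88% and 99.8%.

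**6. Everyone attends the nearest site, all sites offer everything, and distance itself drives the choice** (0.25 / 0.5 / 1 logit per SD of distance, selection 1). The written instrument rejects in 1.5% / 3.6% / 4.6% under no effect, with power 5% / 32% / 85% for a time ratio of 2.0. Here it works, and differential distance fails (F about 0.6 to 2).

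Setting 6 still needs strict exclusion, and the endpoint is time to a repeat procedure, which distance could itself affect. With Var(T) = 0.16, the first-stage slope per SD of distance is √[0.16F/(998 + F)]: 0.073 at F = 34.6 and 0.139 at F = 138.3. A direct 5% effect per SD of distance then biases the log ratio by log 1.05/0.073 = 0.67 or 0.0488/0.139 = 0.35, a factor of about 1.9 or 1.4.

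**The case against.** The strongest reply has four parts.

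**Distance is not wholly a product of treatment choice.** This stands. Residence matters too. Section 12.0 lists each provider's criteria for open surgery as a covariate, which implies some choice within centres, and section 4.0 does not say that a centre offers only one treatment. A reader might infer that the fourth condition fails by construction, or that the analysis must either keep the confounding or have almost no power. The documents do not support either inference: setting 6 shows correct size and up to 85% power.

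**The plan adjusts for measured severity and resources.** Degree of obstruction, scar length, lung function, socioeconomic status and location are to be collected, covariates enter both stages, and instrument–outcome confounding is to be adjusted for where possible. This narrows the problem to residual unmeasured selection, but that residue is the reason for having an IV analysis.

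**The fallback would catch a bad instrument.** Partly so. An F near 4 would show in an ordinary strength check, if one were specified. The biased case has F of 119–169 and would pass.

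**Differential distance may have been meant.** The exclusion sentence speaks of relative distance, so this is possible. But the treating facility is named three times, and the citation numbers at the instrument do not match the section 17.0 list as supplied, so they do not settle it. The text needs correcting on either reading.

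**Conclusion.** The point holds as a defect in how the instrument is defined. In the setting that sections 4.0 and 5.0 and the second hypothesis describe, distance to the treating facility is largely determined jointly with treatment. That conflicts with the plan's fourth condition and with the relative distance in its exclusion assumption. Where patients choose a treatment and travel to it, about all of the unadjusted bias remains. False rejection is roughly 10–50% under moderate selection and reaches 86% at the strongest selection tried. Where the nearest site sets treatment, the instrument is weak, with power below 10% for time ratios of 1.5 and 2.0.

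Confidence is high on the definition and limited on the sizes, which rest on my assumptions about the map, choice strength, confounding, absence of measured covariates and absence of censoring. The instrument is also valid when there is no unobserved selection, but then it is not needed.

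The planned primary analysis is Kaplan–Meier, logrank and Cox. This is therefore a change that should be made to a supporting analysis, not a threat to the whole plan.

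**What to change.** In section 12.0, replace the instrument and add the following:

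- **Definition:** differential distance from residence at diagnosis. This is the distance to the nearest participating centre whose defined standard of care is resection or open surgery, minus the distance to the nearest participating centre whose standard is dilation. It is computed without reference to where the patient was treated.
- **Contrast:** the binary one already in section 12.0, dilation against resection or open surgery. One instrument cannot identify two contrasts among three groups.
- **Checks:** report first-stage F and the balance of measured covariates across the instrument.
- **Exclusion:** state that distance to the treating facility will not be used as an instrument.
- **Status:** label the IV result a sensitivity analysis.

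The cost is SAP wording, a geocoding step from residence and the site list (both already needed for the planned distance), and classification of each centre by its standard of care.

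The downside is possible weakness. If many centres offer every treatment, F was about 0.5 to 2 in simulation. If far-travelled patients concentrate at one dilation referral centre, F was about 15. The latter matters because section 5.0 sets a recruitment target of 750–800 for one institution out of 800–1100 overall, at least 750/1100 = 68%, although remote consent means recruitment there need not be treatment there. If the instrument proves weak, the wide interval should be shown and the IV result reported as uninformative.
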